NCT03728140

Study Protocol & Statistical Analysis

12/01/2019

Objective:

A total of 335 couples participated in this study, which was performed between January 2018 and December 2019 at the Reproductive Medicine Department, Jinan Central Hospital Affiliated to Shandong University, and Reproductive Medicine Center, Gansu Provincial Maternity and Child-care Hospital. The couples underwent ICSI/IVF treatment and their high quality embryos were randomized to embryo transfer using either fresh or self-spent medium with informed consents and ethics approvals.

Design:

Patients met the following criteria were included: (i) ≤ 35 years old; (ii) regular menstrual cycles; (iii) baseline follicle stimulating hormone (FSH) <12 IU/L; (iv) infertility with simple tubal or/and male factors; (v) did not experience more than two prior failed ET cycles; (vi) at least two good-quality Day 3 embryo or one good-quality Day 5 blastocyst for ET. Exclusion criteria were as follows: (i) uterine abnormalities, such as adenomyosis, endometriosis and endometrial polyps; (ii) ovarian abnormalities, such as low ovarian response and polycystic ovary syndrome (PCOS); (iii) endometrial thickness <7 mm on transfer day.

Methods:***Ovarian stimulation and IVF/ICSI procedure***

Controlled ovarian hyperstimulation was carried out with uninterrupted injection of recombinant FSH (Gonal-F; Merck Serono; Switzerland) following pituitary down-regulation by GnRHa. When the dominant follicles measured ≥ 18 mm in diameter, human chorionic gonadotrophin (hCG, Lizhu Inc, China) or recombinant hCG (Ovidrel, Merck Sereno, Switzerland) was administered, and oocyte retrieval was performed approximately 36.5 h later. Sperms were prepared using density gradient centrifugation and swim-up techniques before fertilization, and IVF/ICSI procedures were applied 4–6 h after oocyte retrieval. Fertilization was assessed by checking the appearance of two pronuclei 16–18 h later.

Embryo culture

After fertilization, embryos were cultured one by one in G1TM-PLUS medium drops (Vitrolife, V.Frölunda, Sweden) containing human serum albumin and gentamicin covered with OVOILTM (Vitrolife, V.Frölunda, Sweden) in the culture dish until Day 3, G2TM-PLUS medium was sequential used from Day 3 to Day 6 if the embryos need to blastocyst culture. All mediums for embryo culture were pre-equilibrated at 37°C and 6% CO₂ before use.

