Cleavage stage embryos were morphologically classified according to the number and shape of blastomeres, the percentage of fragmentation as well as multinucleation on Day 3, as following: Grade 1, no or <5% fragmentation with at least six equal-sized blastomeres and no multinucleation; Grade 2, <20% fragmentation with slightly unequal-sized blastomeres and no evidence of multinucleation; Grade 3, 20%–50% fragmentation with obviously unequal-sized cells; and Grade 4, >50% damage or severely unequal-sized cells or visible multinucleation. Blastocysts were classified according to development stage (staging 1-5) and morphology of inner cell mass (Grading A-C) and trophectoderm (Grading A-C).

Embryo transfer

Two Day 3 fresh cleavage stage embryos scored better than grade 2 or single Day 5 fresh blastocyst stage embryo scored better than 4BB was selected for intrauterine transfer. The selected embryos were pre-transferred into a 500 µl pre-equilibrated fresh culture medium (G1TM-PLUS or G2TM-PLUS) awaiting ET. In the test group, the stretched thin Pasteur pipettes were used to absorb the self-spent droplets under the oil, and the droplets were transferred at least three times in a new dish to remove the oil floating on the surface. Then, the selected embryos were transferred to the combined droplet for catheter loading. Correspondingly, the embryos of the control group were loaded directly in the pre-equilibrated fresh culture medium. Luteal support by progesterone administration was provided to the patients after transfer.

Outcome Measures

Chemical pregnancy was confirmed by detecting serum β -hCG level 14 days after embryo transfer, and clinical pregnancy was defined as presence of at least one gestational sac identified by ultrasound 5 weeks after transfer. Biochemical pregnancy rate was defined as the number of early pregnancy losses divided by the total number of positive serum β -hCG. Clinical pregnancy rate was defined as the number of clinical pregnancies divided by the number of transfer cycles. Implantation rate was calculated as the number of gestational sacs divided by the number of embryos transferred. Clinical abortion rate was defined as the number of clinical pregnancy losses before 28 weeks of gestation divided by the total number of clinical pregnancies. Live birth rate was defined as a ratio between healthy living newborns and embryo transfer cycles.

Statistical Analysis:

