Data were analyzed using student's t-test and chi-square test. $P < .05$ was considered statistically significant.

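### The plan's live birth rate counts healthy newborns per transfer cycle, so it is not the proportion of cycles that end in a live birth

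*Combined protocol and SAP*

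**What the plan says.** Outcome Measures defines the endpoint in one sentence: "Live birth rate was defined as a ratio between healthy living newborns and embryo transfer cycles". Nothing there or elsewhere limits a cycle to one count, and *healthy* is not defined.

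The Embryo transfer section allows more than one embryo per cycle: "Two Day 3 fresh cleavage stage embryos scored better than grade 2 or single Day 5 fresh blastocyst stage embryo". Twins are therefore a foreseeable result of Day 3 transfers.

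The neighbouring definitions keep their units consistent. Clinical pregnancy is a yes/no event: "clinical pregnancy was defined as presence of at least one gestational sac identified by ultrasound 5 weeks after transfer". Its rate is per cycle: "Clinical pregnancy rate was defined as the number of clinical pregnancies divided by the number of transfer cycles". Clinical abortion is per pregnancy: "the number of clinical pregnancy losses before 28 weeks of gestation divided by the total number of clinical pregnancies". Biochemical loss is divided by positive tests. Implantation also counts both members of a twin pair, but divides by embryos: "Implantation rate was calculated as the number of gestational sacs divided by the number of embryos transferred".

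The Statistical Analysis section says only "Data were analyzed using student's t-test and chi-square test", with a 0.05 threshold. It assigns neither test to any outcome.

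**The concern.** A reader takes a live birth rate to be the chance that a transfer cycle ends with a live-born child. The stated ratio is the mean number of healthy newborns per cycle, and a cycle can contribute 0, 1 or 2. Of the five rates defined, it is the only one that puts a count of infants over cycles.

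Three things follow.

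- The figure mixes the chance of a live birth with the twin share and with an unstated judgement of health.
- It does not join up with the plan's own clinical pregnancy and abortion rates, and can exceed the clinical pregnancy rate.
- If the ratio were tested as though it were a simple proportion, the test would assume too small a variance whenever some cycles yield two counted newborns.

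**Working it through.** **Inputs from the document.** The definitions above; two Day 3 embryos or one Day 5 blastocyst per transfer; 335 couples (Objective). The document gives no live birth rate, twin share, cycle count, arm sizes or Day 3/Day 5 split, so there is no stated figure to reproduce.

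**Assumptions.** One cycle per couple; arms of 168 and 167; two-sided 0.05; no triplets. L, the share of cycles with a live birth, is 30–60%. t is the twin share of those deliveries. h is the share of live-born infants counted as healthy, independently between infants.

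**1. What the ratio measures.** R = L(1+t)h.

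- Suppose 100 cycles give 40 deliveries, 12 of them twins, with all infants healthy. Newborns = 28 + 24 = 52, so R = 52%, while 40% of cycles had a live birth.
- R falls below L once 1−h exceeds t/(1+t): 0.10/1.10 = 9.1% of infants at 10% twins, 0.20/1.20 = 16.7% at 20% twins.
- At L = 60% and t = 10%, R = 66.0% with h = 1 (+6.0 points) and 59.4% with h = 0.90 (−0.6). At L = 30% the values are 33.0% (+3.0) and 29.7% (−0.3).

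**2. Link to the plan's other rates.** Let C be the clinical pregnancy rate and a the abortion rate. With no losses from 28 weeks on, L = C(1−a), so R = C(1−a)(1+t)h. R exceeds C once t > 1/[(1−a)h] − 1.

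| Assumed a | h = 1 | h = 0.95 | h = 0.90 |
|---|---|---|---|
| 10% | 11.1% | 17.0% | 23.5% |
| 15% | 17.6% | 23.8% | 30.7% |

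Losses from 28 weeks on would raise these thresholds.

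**3. Comparison between arms (h = 1).** R1 − R2 = (L1 − L2) + (L1t1 − L2t2).

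- At equal L, a 10-point difference in twin share gives 0.30 × 0.10 = 3.0 points to 0.60 × 0.10 = 6.0 points.
- With no treatment effect the second term has mean 0 and SD √[Lt(1−Lt)(1/168 + 1/167)]. That is 1.9–2.6 points at 10% twins and 2.6–3.6 points at 20%, over L = 30–60%.

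**4. Size of a chi-square test, if one is applied to newborns over cycles.** With h = 1 and m = L(1+t), the per-cycle variance is L(1+3t) − m², while the test assumes m(1−m). At L = 50% and t = 10%, m = 0.55. The true variance is 0.65 − 0.3025 = 0.3475 against an assumed 0.2475, a ratio of 1.40. The approximate size is 2[1 − Φ(1.96/√1.40)] = 0.098. Simulated sizes (200,000 null trials per cell, no continuity correction):

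| Twin share | L = 30% | 40% | 50% | 60% |
|---|---|---|---|---|
| 0 | 0.050 | 0.049 | 0.048 | 0.049 |
| 5% | 0.066 | 0.069 | 0.072 | 0.082 |
| 10% | 0.083 | 0.086 | 0.096 | 0.115 |
| 20% | 0.113 | 0.124 | 0.146 | 0.187 |

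- With h = 0.90 the mean is hm and the variance is h² times the variance above plus h(1−h)m. At L = 60% the size is then about 0.10 at 10% twins and 0.15 at 20%.
- If 20% is the twin share among Day 3 deliveries only, size is 7–8%, 8–12% and 10–15% when 25%, 50% and 75% of deliveries are Day 3 (h = 1).
- A t-test on newborns per cycle and a chi-square on cycles with a live birth both stay at 0.048–0.051 (h = 1).

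**The case against.** The best defence is that the sentence is loosely worded and deliveries were meant. That is possible, but the text says newborns, and the clinical pregnancy definition beside it shows how the plan writes a per-cycle event. If deliveries were meant, one corrected sentence closes the point.

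The second defence is that the consequences are limited, and much of it stands. A reader might infer any of the following; the document supports none of them.

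- *The live birth comparison is biased.* With no treatment effect the expected gap between arms is zero.
- *The rate is always overstated.* The undefined health criterion can offset the twin effect or outweigh it.
- *The planned test has an inflated false positive rate.* No test is assigned to live birth, and the t-test the plan names holds its level. Inflation needs a chi-square test on newborns over cycles and also some cycles with two counted newborns. A continuity correction, neither stated nor excluded, would reduce it: at 5% twins and h = 1, to 0.052–0.065.
- *The two measures would lead to opposite conclusions.* At h = 1 they differ in sign in about 8–15% of null trials at 5–20% twins. The gap in cycles with a live birth is then small (median 0.4–1.4 points), and at most 0.03% of trials combine opposite signs with a significant chi-square result on either measure.

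**Conclusion.** The point holds on the text: the label says live birth rate, and the rule gives healthy newborns per transfer cycle. This is a wrong rule, not a missing detail, and should be fixed.

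Its size rests wholly on assumed rates. The figure is L(1+t)h instead of L. A 10-point difference in twin share moves the comparison by 3–6 points at L of 30–60% with all infants counted. Only if an uncorrected chi-square is applied to the ratio does its size become about 8–12% at 10% twins and 11–19% at 20% (h = 1), and less as h falls. One cycle per couple and near-equal arms are also assumed.

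It would go too far to say that the trial's main conclusion is affected. No outcome is named primary, and the document does not show which count was tabulated or how it was tested.

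**What to change.** - **Definition.** Define live birth rate as transfer cycles with at least one live-born infant divided by transfer cycles, with one cycle per randomised couple. If any couple contributed more than one cycle, use the randomised couple as the unit.
- **Test.** State in Statistical Analysis that this proportion is compared by chi-square.
- **Separate outcomes.** Report multiple births and newborn health on their own, and define *healthy* there.
- **Transparency.** The document is dated 12/01/2019 and written in the past tense, so say that the definition was changed and when. Keep the present ratio, relabelled *healthy newborns per transfer cycle*, and compare it with the t-test the plan already names.
- **If deliveries were meant,** say so and correct the sentence.

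The cost is one sentence in each of two sections and a disclosure note. Deliveries must be tabulated per cycle, and the document does not say whether they already are. Two figures will be reported, and the proportion of cycles with a live birth may be the lower one.

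### Only unadjusted tests are named although two centres and two transfer types are pooled; stratifying the clinical pregnancy analysis costs almost nothing and gains a little precision

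*Combined protocol and SAP*

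**What the plan says.** The analysis plan is one sentence naming methods, "Data were analyzed using student's t-test and chi-square test", plus a 5% significance threshold (Statistical Analysis). It names no strata, covariates or model, and assigns no test to any outcome.

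Two features of the design could affect pregnancy rates:

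- **Centre.** The Objective section names a hospital department in Jinan and a second site, the "Reproductive Medicine Center, Gansu Provincial Maternity and Child-care Hospital".
- **Transfer type.** Under Embryo transfer, couples receive "Two Day 3 fresh cleavage stage embryos scored better than grade 2 or single Day 5 fresh blastocyst stage embryo".

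On allocation, the Objective section says only that "their high quality embryos were randomized to embryo transfer using either fresh or self-spent medium". The ratio, method, stratification and timing are not given.

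The main outcome considered here comes from Outcome Measures: "Clinical pregnancy rate was defined as the number of clinical pregnancies divided by the number of transfer cycles". It is binary, with one value per transfer cycle.

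**The concern.** When a factor predicts the outcome, a stratified comparison removes its contribution to the variance and corrects any chance imbalance between arms. The crude chi-square test does neither. If pregnancy rates differ clearly by centre or transfer type, the plan gives up some power and reports a slightly wider interval. If the arms happen to differ in their mix, the crude difference carries that shift. If the rates do not differ, nothing is gained.

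Transfer type may be used as a stratum only if the arm could not have influenced it, that is, if it was fixed before allocation. The documents do not settle this. Two places suggest that it was. One exclusion, "endometrial thickness <7 mm on transfer day" (Design), is judged as late as the day of transfer. The test medium comes into play only after embryos are chosen: "Then, the selected embryos were transferred to the combined droplet for catheter loading" (Embryo transfer). Neither proves when allocation took place.

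**Working it through.** **Inputs from the documents:** 335 couples; two centres; two transfer types; clinical pregnancy per transfer cycle; 5% significance level. There is no planned power or target effect to reproduce.

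**Assumed:** two-sided testing, one transfer cycle per couple, simple 1:1 randomisation, overall rates of 45% vs 60%, Day 3 share 60% or 80%, centre split 50/50 or 75/25, and the gaps in pregnancy rate between strata shown below.

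**Simulated power.** There were 100,000 trials per scenario with four centre-by-stage strata. The common odds ratio was solved so that the overall rates stay at 45% and 60%; crude power therefore stays at 78.4% to 78.9%. Power and half-width columns are for 60% Day 3 and centres 50/50. Gain columns are in percentage points and span all the assumed splits. Entries are rounded, so differences between columns can be off by 0.1.

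| Centre/stage gap (points) | Odds ratio | Crude power | CMH power | Gain, both factors | Gain, centre only | 95% CI half-width, Mantel-Haenszel |
|---|---|---|---|---|---|---|
| 0/0 | 1.83 | 78.5% | 78.2% | -0.4 to -0.3 | -0.1 | 10.60 |
| 10/10 | 1.86 | 78.6% | 79.1% | +0.2 to +0.4 | +0.2 to +0.4 | 10.50 |
| 20/20 | 1.93 | 78.6% | 81.5% | +1.9 to +3.0 | +1.2 to +1.5 | 10.18 |
| 30/20 | 2.01 | 78.4% | 83.5% | +3.8 to +5.1 | +3.0 to +3.7 | 9.90 |

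The crude half-width is 10.56 points. By the crude sample-size formula, the two-factor gains at these splits equal about 3.6 couples at 10/10, 26 at 20/20 and 47 at 30/20. Type I error is 4.9% to 5.1% for both tests. A repeat simulation put the low ends at +1.8 (20/20) and +3.1 (30/20), possibly because of which stratum was given the higher rate.

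**Analytic check on the risk-difference scale.** The share of variance explained is R² = [qc(1-qc)dc² + qt(1-qt)dt²] / [p(1-p)], where qc and qt are the centre and transfer-type shares, dc and dt the gaps, and p the overall rate. The variance ratio, adjusted over crude, is (1-R²)(1 + 2/330).

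- No gaps: 1.0061, so the SE ratio is 1.003 and the equivalent N is 335/1.0061 = 333.
- 10/10, p = 0.5, shares 0.5: R² = (0.0025 + 0.0025)/0.25 = 0.02; SE ratio 0.993; equivalent N 340.
- 20/20, same p and shares: R² = (0.01 + 0.01)/0.25 = 0.08; SE ratio 0.962; equivalent N 362, or 27 more couples.

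**If randomisation was in fact stratified on both factors.** In 20,000 simulated trials per setting at an overall rate of 50%, the crude test became mildly conservative: type I error was 4.3% to 4.5% where gaps were 10 to 20 points. At 20/20 with a 15-point effect, power was 79.2% crude and 81.9% CMH.

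**Chance imbalance.** Under simple randomisation the SD of the between-arm difference in Day 3 share s is sqrt[s(1-s) × 4/335]: 5.46, 5.35 and 4.37 points at s = 0.5, 0.6 and 0.8. About 1 trial in 20 exceeds 2 SD. With a 20-point stage gap and s = 0.6, the crude difference then shifts by 2 × 5.35 × 0.20 = 2.1 points. Over the three shares, type I error given a 2-SD imbalance is 5.9% to 6.3% crude and 4.9% to 5.0% CMH. With a 10-point gap it is 5.2% to 5.3% crude and 4.9% to 5.0% CMH.

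**Other outcomes, not part of this gain.** All figures are null simulations of 20,000 trials with 60% Day 3.

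- Implantation is counted per embryo: "Implantation rate was calculated as the number of gestational sacs divided by the number of embryos transferred". At an assumed rate of 35% and within-couple correlation of 0.1 or 0.3, a per-embryo chi-square test has 5.7% or 7.6% type I error. Couple-clustered errors give 5.1% at both.
- Live birth is a ratio of newborns to cycles. With a birth probability of 0.40 and 10% to 30% of Day 3 births being twins, a chi-square test has 7.4% to 12.3%, and a per-cycle t-test 4.9% to 5.2%.

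**The case against.** The case against giving this much weight is strong.

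- **The crude test is legitimate.** An unadjusted comparison of a binary outcome in a randomised trial holds its error rate. This stands; adjustment is an improvement, not the repair of an error.
- **The gain depends on assumed gaps.** At 10-point gaps it is under half a point, and at 5 points or less it is nil. Nothing in the documents supports gaps of 20 or 30 points. This stands, and the 30/20 row should be read as an outer bound.
- **Transfer type may be unusable.** Without proof that it preceded allocation, only the centre-only column applies, and the 26 couples and 10.18-point half-width do not. This stands.
- **The imbalance figures are conditional.** Over all trials the crude error is 5%, and stratified randomisation would largely remove the imbalance argument. That is correct, but the precision argument survives, because the crude test is then conservative.
- **Implantation and live birth are different problems.** They are, and they lend no weight here. The plan does not say which test each receives, so their inflated error rates arise only if a chi-square test is used.
- **It may be too late.** The text is in the past tense, so an adjusted analysis may be post hoc. That restricts how it can be presented; it can still be shown beside the crude result.

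**Conclusion.** The concern holds as a minor point. The plan names only unadjusted tests, and nothing in the document accounts for centre or transfer type. For clinical pregnancy, stratifying by both factors changes power by between -0.4 and +3.0 points for gaps from 0 to 20 points; at the top of that range the SE is 3% to 4% smaller. Stratifying by centre alone changes power by between -0.1 and +1.5 points over the same gaps. Validity is not in question.

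These sizes rest on assumed pregnancy rates, stratum shares and gaps, one cycle per couple and simple 1:1 allocation, none of which the documents state. Use of transfer type rests further on its having been fixed before allocation.

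**What to change.** 1. Analyse clinical pregnancy with a CMH test stratified by centre, and by transfer type as well if that was settled before allocation. State when allocation took place and which version applies.
2. Report the Mantel-Haenszel risk difference with a 95% CI (Sato variance) beside the crude result. Simulated coverage was 94.7% to 94.9%. This keeps the absolute-difference scale, whereas a logistic model would change the target to a conditional odds ratio.
3. As separate matters that stratification does not solve, name the test for each other outcome. For implantation, use couple-clustered standard errors. For live birth, keep the protocol's ratio and use a per-cycle t-test, not a chi-square test. If at least one healthy living newborn per cycle is also analysed, label it as a changed outcome definition and still report the ratio.

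The cost is SAP wording and slightly more analysis; centre and transfer type should be on record for every cycle. The price if the strata do not differ is 0.3 to 0.4 points of power, or 0.1 with centre only. If outcomes have already been seen, label the adjusted analysis as added after the plan.

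### The only planned inference is a P-value judged at .05, with no effect estimate or confidence interval, so the plan cannot say how large a difference is or what a non-significant result excludes

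*Combined protocol and SAP*

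**What the plan says.** The Statistical Analysis section is two sentences long. The first is "Data were analyzed using student's t-test and chi-square test"; the second sets the significance threshold at P below .05. It does not say which test goes with which outcome.

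The Objective section gives the size, "A total of 335 couples participated in this study", and the comparison: embryos were "randomized to embryo transfer using either fresh or self-spent medium". It gives no allocation ratio, superiority or non-inferiority hypothesis, margin, target effect or power.

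Outcome Measures defines five rates: biochemical pregnancy (early loss among hCG positives), clinical pregnancy, implantation, clinical abortion and live birth. Two definitions matter most here. For pregnancy: "Clinical pregnancy rate was defined as the number of clinical pregnancies divided by the number of transfer cycles". For loss, the numerator and denominator are "clinical pregnancy losses before 28 weeks of gestation divided by the total number of clinical pregnancies". Neither section asks for a between-arm effect measure or an interval for any of the five.

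**The concern.** Under this plan each outcome ends with one of two labels, significant or not. A chi-square P-value does not show the size of a difference, and when it is above .05 it does not show which differences the data still allow. No margin or power statement is available to fill that gap.

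This bears on both possible conclusions about self-spent medium. If it helps, the reader needs to know by how much. If the result is null, the reader needs to know whether a worthwhile gain, or a harmful fall in pregnancy or rise in loss, has been ruled out. The question is sharpest for clinical loss, because its denominator is clinical pregnancies and so is well below 335.

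**Working it through.** The plan states no power, margin or target effect, so there is no figure to reproduce. The check is what a 95% interval would show beside a non-significant P.

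**Inputs.** From the documents: 335 couples, two arms, threshold .05, and the rate definitions. Assumed, because the documents are silent: 1:1 allocation (168 vs 167), one transfer cycle per couple, a two-sided chi-square test without continuity correction, control pregnancy rates of 30% to 70%, and control loss rates of 8% to 20%.

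**Clinical pregnancy, equal observed rates.** Half-width = 1.96 × √[p(1−p)(1/168 + 1/167)].
- p = .50: 1.96 × .0546 = 10.7 points.
- p = .30 or .70: 1.96 × .0501 = 9.8 points.
- By Newcombe's method, 84/168 vs 83/167 gives −10.3 to +10.9 points.
- Other splits widen this slightly: at p = .50, 10.9 points for 3:2 and 11.3 for 2:1.

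**Clinical pregnancy, just short of significance.**
- 102/168 (60.7%) vs 84/167 (50.3%): difference 10.4 points, P = .055, Newcombe interval −0.2 to +20.7 points.
- One more event, 103/168, gives P = .042. Two nearly identical results would get opposite labels.
- Across control rates of 30% to 70%, the largest non-significant fall is about 9 to 11 points, and its interval reaches about 18 to 22 points.

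**Power for pregnancy** (normal approximation, control rates 30% to 70%):

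| True fall | Power |
|---|---|
| 20 points | about 96% to nearly 100% |
| 15 points | 79% to 91% |
| 10 points | 45% to 56% |

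**Clinical loss, equal observed counts.** At a 50% pregnancy rate there are about 84 pregnancies per arm. With e losses per arm, the risk-ratio interval is exp(±1.96 × √[2/e − 2/84]).

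| Losses per arm | Rate | 95% CI for risk ratio |
|---|---|---|
| 8/84 | 9.5% | 0.39 to 2.54 |
| 10/84 | 11.9% | 0.44 to 2.28 |
| 13/84 | 15.5% | 0.49 to 2.03 |
| 17/84 | 20.2% | 0.55 to 1.82 |

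Varying the pregnancy rate from 40% to 70% (67 to 117 pregnancies per arm), the upper limit runs from 3.3 (5/67, nominal 8% loss) down to 1.68 (23/117, nominal 20%).

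**Clinical loss, just short of significance.** 17/84 vs 8/84 gives P = .051, risk ratio 17/8 = 2.13, interval 0.97 to 4.65. In every scenario checked, a result just short of significance has an upper limit of about 2.5 or more.

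**Power against a true doubling of loss.** About 30% to 67% for control loss of 8% to 12%, and 72% to 92% at 20%.

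**The case against.** The strongest reply is that this is a reporting gap and not lost information. Each rate has a defined numerator and denominator, so once arm counts are published anyone can subtract, and for a binary per-cycle outcome compute an interval. That is true, and it is why the remedy is cheap. But the plan commits to neither the difference nor the interval, and its decision rule uses only P.

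Four stronger readings are tempting and are not supported:

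- **A null pregnancy result generally leaves a 20-point gap open.** It does so only when the observed gap is already about 10 points. Equal observed rates exclude 20 points, and a true fall of that size would be detected about 96% of the time or more.
- **A doubling of loss always stays possible.** At 17/84 in each arm the upper limit is 1.82, so equal counts exclude a doubling if loss is near 20%. At about 10% they do not.
- **P at or above .05 would be presented as no difference or as safe.** The documents say no such thing. They give no rule for reading a null result in either direction, so this is a risk and not a stated intention.
- **Only the loss outcomes could reveal harm.** Lower clinical pregnancy, implantation or live birth in the test group would be harm too. Clinical pregnancy and live birth use transfer cycles as the denominator, which is larger than the number of pregnancies.

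**Conclusion.** The concern holds as a gap in analysis and reporting that should be corrected. A P-value against .05 is the only planned inference, and nothing in the documents lets a reader judge the size of an effect or the meaning of a null result.

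On size: for clinical pregnancy, a non-significant result leaves about 10 to 11 points unexcluded with equal observed rates, and up to about 20 points just short of significance. For clinical loss with equal counts, the upper risk-ratio limit is about 2.5 at 10% loss and 1.8 at 20%, so a doubling may or may not be excluded. These figures rest on assumed 1:1 allocation, one cycle per couple and, for loss, 84 pregnancies per arm. The absence of any effect measure or interval rests on none of these assumptions.

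**What to change.** Replace the P-only rule with the following.

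1. For each couple-level binary outcome, report both arm proportions, the absolute difference (test minus control) with a Newcombe 95% interval, and the risk ratio with a 95% interval. Give the chi-square P alongside and base the conclusion on the interval.
2. State that P at or above .05 will not be reported as no difference, equivalence or safety, and that the interval shows which differences remain compatible with the data.
3. Implantation (sacs per embryo, with two embryos in Day 3 transfers) and live birth (newborns per cycle) are not couple-level proportions. Use an interval that allows for more than one embryo or newborn per couple, for example a couple-clustered robust or bootstrap interval.
4. Loss rates are conditional on pregnancy, which is a post-randomisation subset. Say so, and also give loss per transfer cycle, which keeps the randomised denominator.

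This needs no new data, so it can still be applied when the results are reported. The cost is a few sentences, a slightly longer table and a more cautious conclusion if results are null.
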